10. SAFETY/DEVICE ASSESSMENT

10.1 Adverse Events

Subjects will be carefully monitored during the study for possible device related adverse events (AEs). The investigator or designee will determine AE occurrences and collect the required data. It is anticipated that the occurrence of device related adverse events will be a low number. All device related adverse events will be reviewed not only by the site investigator, but also by the sponsor's medical officer.

Serious Adverse events will be collected during the 72 hour (+ 48 hours) treatment period in the following areas: Cardiac, CNS, pulmonary, renal, and skin disorders.

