## 5 SAMPLE SIZE

Subjects will be randomly assigned in a 2:1 ratio to treatment with Starling SV or to treatment with standard of care, stratified by time window of enrollment (0-6 hours, 6-12 hours, and 12-24 hours). The primary effectiveness endpoint for this study is fluid balance at ICU discharge.

Minimum enrollment ( $N_{\min}$ ) in the study will be set at 120 subjects (80 Starling SV and 40 control) to power at 80% for demonstration of superiority of means for the secondary endpoint of creatinine levels as a measurement of change from baseline at 72 hours. The secondary endpoint for change in creatinine levels at 120 evaluable subjects displays 80% power at a two-sided alpha level of 0.05 to demonstrate superiority of Starling SV under an assumption of an average treatment effect of -1.4 mg/dL with a standard deviation of 2.5 mg/dL.

Under an assumption of an average treatment effect of -2 L with a standard deviation of 3 L, the sample size of 120 evaluable subjects provides 92.7% power in a test of superiority of means for the primary effectiveness endpoint at a two-sided 0.05 level of significance.

The trial will incorporate a sample size re-estimation (SSR) at the time of the interim look (after 90 patients have been evaluated for the key secondary endpoint) based on promise for superiority in the key secondary endpoint. Sample size re-estimation, described in further detail in Section 3.1, will result in a maximum of 210 total evaluable subjects, or no more than 1.75 times the minimum of 120.

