#### 9.2.1.2 Requirement for Renal Replacement Therapy (RRT)

The hypotheses of interest relating to RRT are as follows:

$$H_0: P_t = P_c$$

$$H_1: P_t \neq P_c$$

where  $P_t$  and  $P_c$  represent the proportion of subjects requiring RRT in the treatment and control groups, respectively. Treatments will be compared using the chi-square test. Subjects that enter the study on dialysis, or are on chronic dialysis, are excluded from this endpoint. Summary of this endpoint will include the number and percentage of patients requiring RRT, a 95% confidence interval for the risk difference in the two arm percentages calculated using the normal

approximation to the binomial distribution, and the p-value from the test described above. If the observed event rates are less than 10% in either treatment group, a Fisher's exact test will be used to compare treatments instead of the chi-square test, and the 95% confidence of the risk difference will be based on the Wilson method instead of the normal approximation to the binomial distribution.

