### 9.2.2 NOT FOR FORMAL TESTING

#### 9.2.2.1 Incidence of Treatment Emergent Adverse Events (AE)

A Treatment Emergent Adverse Event (TEAE) is one that started or worsened in severity during or after randomized treatment was attempted. The number and percentage of patients with incidence of at least one TEAE will be summarized by treatment arm in a table. The summary will include the number and percent of subjects experiencing one or more AEs cumulatively up to 72 hours, one week, and 30 days. Though no formal hypothesis tests are planned, 95% confidence intervals for the difference in rates between the two arms at each time point will be completed and included using the normal approximation to the binomial distribution.

The analysis will be repeated for serious TEAS. In addition, the number and percentage of patients with at least one TEAEs will be presented by severity and relationship to study procedure; patients with more than one TEAE will be categorized according to the maximum severity and maximum relationship experienced.

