#### 9.2.2.2 Number of ICU Readmissions

The number of ICU readmissions through 30 days will be summarized by treatment arm in a table. The summary will include the number and percent of subjects with 0, 1, or >1 ICU readmissions. Though no formal hypothesis tests are planned, 95% confidence intervals for the difference in rates between the two arms will be completed and included using the normal approximation to the binomial distribution or Wilson method (if an observed rate is less than 10% in any treatment group).

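### SAP 9.2.2.1 omits the low-rate switch to the Wilson method that every other risk difference in the SAP has; if few adverse events are observed, the interval can collapse or mislead (minor)

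*SAP*

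**What the plan says.** SAP 9.2.2.1 summarises the proportion of patients with at least one TEAE, cumulatively to 72 hours, one week and 30 days. It promises "95% confidence intervals for the difference in rates between the two arms at each time point" and names one method only: they "at each time point will be completed and included using the normal approximation to the binomial distribution". The same paragraph says "Though no formal hypothesis tests are planned", and the next begins "The analysis will be repeated for serious TEAS", so serious TEAEs inherit the method.

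The other binary endpoints are handled differently:

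- ICU readmissions (9.2.2.2) use the normal approximation "or Wilson method (if an observed rate is less than 10% in any treatment group"). Mortality (9.2.2.3), MACE (9.2.2.5) and discharge location (9.2.2.6) carry the same rule.
- RRT (9.2.1.2) says "If the observed event rates are less than 10% in either treatment group, a Fisher's exact test will be used", with a Wilson interval in place of the normal one. Ventilator use (9.2.1.3) matches it.

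SAP 10 and 10.1 add adverse-event counts and percentages but no other interval method. On rates, Protocol 10.1 says only "It is anticipated that the occurrence of device related adverse events will be a low number". That concerns device-related events.

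**The concern.** The normal-approximation interval estimates its own width from the observed proportions. When an arm has no events, that arm contributes nothing to the standard error; when both have none, the width is zero. The SAP guards against this for six endpoints and leaves it unguarded for any-TEAE and serious-TEAE. Because no adverse-event test is planned, these intervals are the only between-arm inference stated for those two outcomes.

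The control arm is small. At 40 patients, an observed rate below 10% means three events or fewer; at 80 it means seven or fewer. If counts fall in that range, the table could show an interval with false precision, or one that excludes zero on very few events.

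**Working it through.** **Inputs.** Arm sizes: the minimum enrolment is "set at 120 subjects (80 Starling SV and 40 control"), in SAP 5. The maximum of 210 at 2:1 gives 140:70. Level: 95% two-sided, z = 1.96 (SAP 9.2.2.1). Event rates: none given, so true rates of 1% to 10% per arm are assumed, with 20% to 50% for contrast. The SAP does not say how Wilson is applied to a difference; it is read here as the Wilson-score (Newcombe) interval. Adverse events are analysed in the mITT and Safety sets (SAP 10), so actual arm sizes may differ somewhat from these.

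**The plan's own figure.** SAP 9.2.2.1 states no rate or precision to reproduce. The 80:40 base can be confirmed from the primary-endpoint power in SAP 5. The noncentrality is 2 / (3 × √(1/80 + 1/40)) = 3.44, and the noncentral t with 118 df gives 92.7%, as stated.

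**Formulas.** With d = p1 - p2 (Starling SV minus control):

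- Normal: d ± 1.96 × √(p1(1-p1)/n1 + p2(1-p2)/n2).
- Newcombe, where (l, u) are the Wilson limits for each arm: lower = d - √((p1-l1)² + (u2-p2)²); upper = d + √((u1-p1)² + (p2-l2)²).

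**No events in either arm.** Normal: the standard error is 0, so the interval is 0 to 0 at any N. Newcombe: with zero events the Wilson upper limit is z²/(n+z²).

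- 80:40: 3.84/83.84 = 4.6% and 3.84/43.84 = 8.8%, so -8.8 to +4.6 points.
- 140:70: 3.84/143.84 = 2.7% and 3.84/73.84 = 5.2%, so -5.2 to +2.7 points.

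The chance of 0 v 0 at 80:40 is (1-p)^120 for a common rate p: 30% at 1%, 9% at 2%, 0.2% at 5%.

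**4/80 v 0/40.** d = 5.0 points.

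- Normal: SE = √(0.05 × 0.95/80 + 0) = 2.44 points, giving +0.2 to +9.8. Zero is excluded.
- Newcombe: the Wilson limits are 1.96% to 12.16% for 4/80 and 0 to 8.76% for 0/40. Lower = 5.0 - √(3.04² + 8.76²) = -4.3; upper = 5.0 + 7.16 = +12.2. Fisher's exact test gives p of about 0.30, in line with this interval.

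**Exact coverage of the nominal 95% intervals**, by enumerating both binomials:

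| True rate, Starling v control | Normal, 80:40 | Newcombe, 80:40 | Normal, 140:70 | Newcombe, 140:70 |
|---|---|---|---|---|
| 1% v 3% | 70.1% | 98.3% | 87.4% | 97.7% |
| 2% v 5% | 86.6% | 98.4% | 90.9% | 96.5% |
| 1% v 1% | 99.4% | 99.6% | 97.2% | 99.0% |
| 3% v 3% | 93.0% | 98.1% | 91.2% | 97.0% |
| 5% v 5% | 91.3% | 97.2% | 93.0% | 96.3% |
| 2% v 1% | 86.2% | 98.8% | 95.6% | 98.3% |
| 3% v 1% | 92.9% | 99.3% | 97.0% | 97.7% |
| 5% v 2% | 95.8% | 96.8% | 95.7% | 96.9% |
| 10% v 10% | 93.6% | 95.8% | 94.1% | 95.6% |

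At equal rates of 20% to 50% the normal interval covers 93.9% to 94.3% at 80:40, which is adequate. At 1% v 1% its high coverage is partly an artefact: the true difference is zero, so a collapsed 0 to 0 interval counts as a hit.

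**The case against.** The strongest reply is that the harm may never occur. The population has sepsis with refractory hypotension, death is a serious adverse event (Protocol 10.1.2), and a proportion with at least one event pools all event types. Such proportions may well exceed 10%. A reader might take the Protocol 10.1 remark about low numbers as evidence that these rates will be low. It is not: it concerns device-related events, for which the SAP states counts and percentages but no interval. Equally, nothing shows the rates will be high. Protocol 10.2.1 requires the adverse-event form for device-related events, and Protocol 10.1 limits serious-event collection to five areas over 72 hours plus 48. So the point stands only as a conditional one.

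A reader might also infer from the 70.1% figure that the normal interval generally under-covers at low rates. The table does not support that. The figure is the worst of the pairs examined, it applies when Starling SV has the lower rate, and it rises to 87.4% at 140:70. Where Starling SV has the higher rate, coverage at 80:40 is mixed: 86.2% at 2% v 1%, 92.9% at 3% v 1% and 95.8% at 5% v 2%.

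Finally, a reader might infer that the report would declare near certainty of equal safety. Nothing in the SAP draws that conclusion. The section is outside formal testing, the counts stand beside the interval, and mortality and MACE already have the Wilson rule. These replies lower the severity. They do not explain why this one section lacks the rule.

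**Conclusion.** The omission is real and is inconsistent with the SAP's own practice for its six other risk differences. Its consequence depends on observed any-TEAE or serious-TEAE rates being low, which the documents neither state nor rule out. If they are low, the stated method can give a zero-width interval (0 v 0, at any N) or one that excludes zero on four events (4/80 v 0/40), and coverage can fall well below 95% for some pairs of true rates. The error is not always reassuring: the 4 v 0 example would suggest an excess on Starling SV that the data do not establish. If both rates are about 20% or more, the present method is adequate.

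These sizes rest on arms of 80:40 or 140:70, assumed true rates, and Wilson read as the Newcombe interval. That interval covers at least 95.6% in every pair examined with both rates at or below 10%. No test or decision depends on the affected intervals, so this is a minor consistency correction.

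**What to change.** In SAP 9.2.2.1, add the rule already in 9.2.2.2, 9.2.2.3, 9.2.2.5 and 9.2.2.6: use the Wilson method if an observed rate is below 10% in any treatment group. State that for a difference this means the Wilson-score (Newcombe) interval. Apply it to all TEAEs and to serious TEAEs at each time point, and add it before unblinded adverse-event counts are seen, so that the method is not chosen on the results.

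The cost is one sentence. The descriptive intervals will generally be wider when rates are low and unchanged when both observed rates are 10% or more. No endpoint, population, sample size or trial procedure changes.

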#### 9.2.2.2 Number of ICU Readmissions

The number of ICU readmissions through 30 days will be summarized by treatment arm in a table. The summary will include the number and percent of subjects with 0, 1, or >1 ICU readmissions. Though no formal hypothesis tests are planned, 95% confidence intervals for the difference in rates between the two arms will be completed and included using the normal approximation to the binomial distribution or Wilson method (if an observed rate is less than 10% in any treatment group).

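### SAP 9.2.2.2: the switch to Wilson is triggered only by rates below 10%, so, read row by row, a '0 readmissions' row above 90% keeps a normal-approximation interval that usually under-covers

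*SAP*

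**What the plan says.** SAP 9.2.2.2 (Number of ICU Readmissions) defines three rows: "The summary will include the number and percent of subjects with 0, 1, or >1 ICU readmissions". On the comparison it says that "95% confidence intervals for the difference in rates between the two arms will be completed", "using the normal approximation to the binomial distribution" or by the "Wilson method (if an observed rate is less than 10% in any treatment group"). The same sentence opens with "Though no formal hypothesis tests are planned", and the endpoint sits under the heading for endpoints outside formal testing.

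No section adds a trigger for rates above 90%. None says whether the observed rate is checked separately for each row or once for the table, and none gives an expected readmission rate. The same trigger wording appears in 9.2.2.3 (mortality), 9.2.2.5 (MACE) and 9.2.2.6 (discharge location).

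On arm sizes, SAP section 5 says that minimum enrollment "will be set at 120 subjects (80 Starling SV and 40 control"), and that re-estimation "will result in a maximum of 210 total evaluable subjects".

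**The concern.** The variance p(1-p)/n is symmetric about 50%, so the normal approximation is as poor at 95% as at 5%. By switching at low rates the SAP accepts that the approximation fails near a boundary, but it guards only one boundary. This table includes a row that lies near the other one whenever readmission is uncommon. Rows '1' and '>1' then move to Wilson while row '0' does not.

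What is at stake is the accuracy and internal consistency of published 95% intervals. The endpoint has no p-value, so the interval is the only measure of uncertainty that a reader gets.

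**Working it through.** **Inputs.** Arms of 80 and 40 are from SAP section 5. Arms of 140 and 70 follow from the maximum of 210 at 2:1 (210 × 2/3 and 210 × 1/3). Section 9.2.2.2 states no computed figure to reproduce. As a check on the arm sizes, a noncentral t calculation with 80 v 40, effect 2 L, SD 3 L and two-sided 0.05 gives 92.71% power, against the SAP's 92.7%. True rates in row '0' are my assumption, 92% to 98%. I take Wilson for a difference to mean the Newcombe hybrid-score interval. Differences are Starling SV minus control.

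**Formulas.**
- Normal approximation: d ± 1.96 × √[p1(1-p1)/n1 + p2(1-p2)/n2], with d = p1 - p2.
- Newcombe, with (l, u) the Wilson limits of each arm: lower = d - √[(p1-l1)² + (u2-p2)²]; upper = d + √[(u1-p1)² + (p2-l2)²].
- Coverage: the sum of Bin(x; n1, p1) × Bin(y; n2, p2) over all (x, y) whose interval contains the true difference.

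**Step 1: coverage of row '0' under the row-by-row rule.**

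| True '0' rates | SAP rule 80:40 | Newcombe 80:40 | SAP rule 140:70 | Newcombe 140:70 |
|---|---|---|---|---|
| 98%/98% | 96.4% | 98.8% | 91.8% | 97.7% |
| 97%/97% | 93.0% | 98.1% | 91.2% | 97.0% |
| 96%/96% | 91.4% | 97.6% | 92.2% | 96.5% |
| 95%/95% | 91.3% | 97.2% | 93.0% | 96.3% |
| 92%/92% | 93.0% | 96.3% | 93.8% | 95.8% |

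With unequal rates at 80:40, the SAP rule gives 89.7% at 96%/94%, 86.6% at 98%/95% and 95.4% at 95%/97%.

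**Step 2: disagreement between rows.** Suppose 4/80 v 0/40 subjects are readmitted, once each.
- Row '0' (76/80 v 40/40, normal approximation): d = -5.0 points; SE = √(0.95 × 0.05/80) = 2.44 points; 1.96 × 2.44 = 4.78. The interval is -9.8 to -0.2, which excludes zero.
- Row '1' (4/80 v 0/40, Wilson): the Wilson limits are 1.96% to 12.16% and 0% to 8.76%. Lower = 5.0 - √(3.04² + 8.76²) = 5.0 - 9.27 = -4.3. Upper = 5.0 + 7.16 = +12.2. The interval includes zero.

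The same patients give opposite readings. The direction can also reverse: with 0/80 v 3/40, row '0' by normal approximation is -0.7 to +15.7, while the Wilson-based interval on the same scale is +0.8 to +19.9.

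**Step 3: nobody readmitted.** With 0/80 v 0/40, p(1-p) = 0 in both arms of row '0', so the interval is 0 to 0. Newcombe gives -4.6 to +8.8.

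**Step 4: how often.** Take the tables with at most 10% readmitted in both arms and under 10% in at least one. The normal-approximation interval for row '0' is narrower than Newcombe in all 44 at 80:40 and all 119 at 140:70. It disagrees about zero with its complement (any readmission) in 7 of 44 and 16 of 119. Weighted by the same binomial probabilities at 80:40, the chance of disagreement is 4.4% to 9.5% over equal true rates of 92% to 98%.

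**Step 5: the table-wide reading.** If an arm has more than 90% in row '0', less than 10% is left for rows '1' and '>1' together, so each is below 10%. A table-wide trigger then fires and every row uses Wilson.

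**The case against.** The strongest objection is that the sentence is ambiguous. On a table-wide reading it already protects row '0', as step 5 shows. That stands. The row-by-row reading is the more natural one, because the condition ranges over treatment groups and attaches to each difference between arms. But the SAP does not settle it, and two programmers could produce different intervals from the same data.

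Three stronger readings are tempting, and the documents do not support them.
- A reader might infer that the '0' row interval will be too narrow. That needs more than about 90% without readmission in both arms, and no rate is given. Even then under-coverage is not universal: 98%/98% and 95%/97% are adequate at 80:40.
- A reader might infer that the table will contradict its own mirror image. There is no planned row for one or more readmissions. Row '1' complements row '0' only if no subject has more than one. The 4/80 v 0/40 example is also borderline, with an upper limit of -0.2, and 0/80 v 0/40 has probability 0.95^120 = 0.2% at a 5% readmission rate and 0.98^120 = 9% at 2%.
- A reader might infer equal harm wherever the wording recurs. For mortality and MACE the gap matters only if an event rate exceeds 90%, and nothing suggests that. For discharge location it matters only if one category dominates.

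Finally, the endpoint is descriptive. Reading a test into whether an interval excludes zero goes beyond what the SAP plans.

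**Conclusion.** The concern holds in a limited form. The trigger is one-sided and its unit is unstated. Read row by row, and assuming that more than about 90% of subjects in both arms have no readmission, the '0' row usually under-covers: 91.3% at 95%/95% and 89.7% at 96%/94% for 80:40, and about 91% to 94% at equal rates of 92% to 98% for 140:70, so the larger sample does not cure it. The interval collapses to zero width if nobody is readmitted, and it can disagree with row '1' about zero when all readmissions are single. Under a table-wide trigger none of this arises. No formal test, multiplicity step or primary result is affected. Severity is low, but the sentence is worth correcting before database lock.

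**What to change.** In SAP 9.2.2.2, and in 9.2.2.6 where one discharge category may dominate, use the Wilson-based (Newcombe) interval for the risk difference in every row. The minimum alternative is to change the trigger to a rate less than 10% or greater than 90% in any treatment group, and to state that it is applied row by row. Either way, complementary rows whose rates meet the trigger become exact mirrors: with 4/80 v 0/40, row '0' becomes -12.2 to +4.3. The same wording in 9.2.2.3 and 9.2.2.5 may be aligned, for consistency only.

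The change is one sentence and needs no new data. The real cost is width. In the 4/80 v 0/40 example row '0' goes from 9.6 to 16.4 points, and with 2/80 v 1/40 from 11.9 to 17.0. The new intervals are somewhat conservative, with coverage of about 96% to 99% over the rates examined.

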#### 9.2.2.3 Mortality Rate

The mortality rate will be summarized by treatment arm in a table. The summary will include the number and percent of subjects who died by arm; Kaplan-Meier mortality curves will be presented for each treatment group. Though no formal hypothesis tests are planned, 95% confidence intervals for the difference in rates between the two arms will be completed and included using the normal approximation to the binomial distribution or Wilson method (if an observed rate is less than 10% in any treatment group).

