3. SYNOPSIS

Title:	Evaluation of fluid volume in patients with sepsis and refractory hypotension
Short Title:	FRESH (Fluid Responsiveness Evaluation in Sepsis-associated Hypotension) Fluid Trial
Investigational Device:	Noninvasive Starling™ SV
Objective:	To assess the mean difference in fluid balance and associated patient outcomes, based on a dynamic assessment of fluid responsiveness in septic patients with refractory hypotension in an ICU setting.
Design:	
Multi-center randomized study comparing dynamic assessment of fluid responsiveness utilizing Starling SV compared to a control group.
 
Subjects will be randomized in a 2:1 treatment to control group ratio to increase power for sub-analysis by patient population.
 
Patients randomized to the Starling SV arm will have treatment guided by a dynamic assessment of fluid responsiveness (measured by a change in stroke volume index > +10%) as assessed by passive leg raise (PLR).
 
Patients randomized to the control group will receive standard of care treatment. The use of dynamic fluid assessment (i.e. SVV, PPV, or SV change) to determine fluid responsiveness is prohibited.

Primary Endpoint:	Mean difference in fluid balance (L) at 72 hours or ICU discharge, whichever occurs first, between the two treatment groups
Secondary Endpoints	
 1. Length of ICU stay (days) until subject is medically ready for discharge 2. Number of hours free from ventilator use 3. Requirement for mechanical ventilation 4. Number of hours free from vasopressor use 5. Changes in serum creatinine levels from baseline 6. Requirement for renal replacement therapy (RRT) 7. Mean volume of fluid between the two treatment groups 8. Incidence of Major Adverse Cardiac Event (MACE) 9. Incidence of Adverse Events (AE) 10. Number of ICU readmissions 11. 30 day in-hospital mortality rate 12. Discharge location 13. Mean difference in fluid balance at ICU discharge

Planned Enrollment:	Approximately 210 subjects will be involved in the analysis population
Population:	Patients with sepsis who exhibit refractory hypotension (MAP < 65, or require treatment with vasopressors to maintain a MAP > 65) following initial fluid resuscitation (1L of fluid).
Follow-up Schedule:	Hemodynamic data collection will occur for a 72 hour period starting at the time of study enrollment. Subject outcome data will be collected until the time of hospital discharge.

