## 2 SUMMARY

TITLE	Evaluation of fluid volume in patients with sepsis and refractory hypotension.
PREFACE	
This Statistical Analysis Plan (SAP) describes the planned analysis and reporting for Cheetah Medical, Inc. protocol PRO-0001 (Fluid Responsiveness Evaluation in Sepsis-associated Hypotension [FRESH] Fluid Trial). This study is being completed to assess the safety and efficacy in using Starling SV for dynamic assessment of fluid responsiveness in the treatment of septic patients with refractory hypotension.
 
The following documents were reviewed in preparation of this SAP:
 
 
• Clinical Research Protocol PRO-0001, issued 30OCT2017
 
• Case report forms (CRFs) issued 01DEC2017 for Protocol PRO-0001
 

PURPOSE	The purpose of this SAP is to outline the planned analyses in support of the Clinical Study Report (CSR) for protocol PRO-0001. Exploratory analyses not necessarily identified in this SAP may be performed to support the clinical development program. Any post-hoc, or unplanned, analyses not identified in this SAP will be clearly identified in the respective CSR or manuscript.
STUDY OBJECTIVES	The objective of this study is to assess the mean difference in fluid balance at 72 hours or ICU discharge, whichever occurs first, and associated patient outcomes, based on a dynamic assessment of fluid responsiveness in septic patients with refractory hypotension in an ICU setting.
STUDY ENDPOINTS	
Primary: Fluid balance (L) at 72 hours or ICU discharge, whichever occurs first
 
Secondary:
 
 
1. Changes in serum creatinine level from baseline to 72 hours (key secondary endpoint)
 
2. Requirement for renal replacement therapy (RRT)
 
3. Requirement for ventilator use
 
4. Length of ICU stay (days) until subject is medically ready for discharge
 
5. Number of hours with ventilator use (30-day period)
 
6. Number of hours with vasopressor use
 
 
Not for Formal Testing:
 
 
1. Incidence of Adverse Events (AE)
 
2. Number of ICU readmissions
 
3. 30 day in-hospital Mortality rate
 
4. Volume of Treatment Fluid
 
5. Incidence of MACE
 
6. Discharge location
 
7. Mean difference in fluid balance at ICU discharge
 

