STUDY DESIGN	This study is a prospective, multi-center, randomized trial comparing the mean difference in fluid balance and associated patient outcomes between a treatment guided by a dynamic assessment of fluid responsiveness and a standard of care control group not using dynamic fluid assessment.

	
Subjects will be randomized in a 2:1 treatment to control group ratio to increase power for sub-analysis by patient population. Subject randomization will be stratified by time window of enrollment to ensure even randomization between the three time windows of enrollment (0-6 hours, 6-12 hours, and 12-24 hours).
 
Patients randomized to the Starling SV arm will have treatment guided by a dynamic assessment of fluid responsiveness (measured by a change in stroke volume index > 10%) as assessed by passive leg raise (PLR).
 
Patients randomized to the control group will receive standard of care treatment. The use of dynamic fluid assessment (i.e. SVV, PPV, or SV change) to determine fluid responsiveness within the control group is prohibited.

INTERIM ANALYSES	
An interim analysis is planned after 90 subjects have been enrolled and completed the evaluation of the key secondary endpoint of change in serum creatinine at 72 hours. At this analysis, a sample size re-estimation will occur in order to determine promise for superiority in the key secondary endpoint.
 
No annual reports for the FDA are anticipated prior to the end of data collection as this study is not intended to support a regulatory filing.
 
An annual report and project status update may be requested by the local IRB at study sites.
 
No other interim analyses are planned.

FINAL ANALYSES	
All final planned analyses identified in this SAP will be completed after the last subject has completed their 30 day follow up.

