#### 4.2.2.2 Not for formal testing

Additional exploratory secondary endpoints identified for testing, but will not be included in the formal statistical testing procedures for key secondary endpoints are:

- Incidence of Adverse Events (AE)
- Number of ICU readmissions
- Mortality rate
- Volume of treatment fluid
- Incidence of Major Adverse Cardiac Event (MACE)
- Discharge location
- Mean difference in fluid balance at ICU discharge

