#### 9.2.2.5 Incidence of Major Adverse Cardiac Event (MACE)

The incidence of MACE through to 72 hours, one week, and 30 days will be summarized by treatment arm in a table. The summary will include the number and percent of subjects by arm by category. Though no formal hypothesis tests are planned, 95% confidence intervals for the difference in rates between the two arms will be completed and included using the normal approximation to the binomial distribution or Wilson method (if an observed rate is less than 10% in any treatment group). Kaplan-Meier curves of time to first component of MACE will be presented by treatment group.

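### The Kaplan-Meier mortality curves have no censoring rule for discharge alive; if survivors are censored at discharge, the curves overstate 30-day in-hospital mortality

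*SAP*

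**What the plan says.** **Analysis.** For mortality, SAP 9.2.2.3 plans a table ("The summary will include the number and percent of subjects who died by arm"), an interval ("Though no formal hypothesis tests are planned, 95% confidence intervals for the difference in rates between the two arms will be completed") and a graph ("Kaplan-Meier mortality curves will be presented for each treatment group"). The interval is binomial (normal approximation) or Wilson. The section gives no time origin, horizon or censoring rule. The protocol synopsis (Statistical Design) makes Kaplan-Meier the method for any survival analysis. Neither document names a competing-risk method.

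**Endpoint.** SAP Section 2 lists "30 day in-hospital Mortality rate", and Protocol 7.3.2 agrees. SAP 4.2.2.2 lists only "Mortality rate", with no setting and no window.

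**Follow-up.** The protocol synopsis says: "Subject outcome data will be collected until the time of hospital discharge". The last column of the schedule of assessments (Protocol 9.4, Table 1) ends at discharge. SAP Section 2, however, places the final analysis "after the last subject has completed their 30 day follow up", and SAP 3.2 says the same. SAP 10.1 tabulates adverse events between discharge and day 30.

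**MACE.** SAP 9.2.2.5 states: "Kaplan-Meier curves of time to first component of MACE will be presented by treatment group". The components are not defined in either document.

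**The concern.** Kaplan-Meier assumes that a censored subject keeps the same risk of the event as those still under observation. For in-hospital death this fails by definition at discharge alive: the subject can no longer die in hospital, barring readmission. Discharge alive is therefore a competing event. Censoring at that point yields the mortality of a hypothetical hospital that nobody leaves alive.

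Two things are at stake. First, a curve could end well above the crude percentage printed beside it, on the outcome that readers will look at first. Second, the visual comparison between arms could mislead if the arms discharge at different speeds. That is plausible here, because shorter ICU stay is one of the formally tested secondary endpoints (SAP 7.5 and 9.2.1.4), although ICU stay is not the same as hospital stay.

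**Working it through.** The documents state no figure for mortality, length of stay or post-discharge death, so there is nothing of the plan's to reproduce. Every rate below is an assumption, used to show direction and range.

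**1. Formulas.** Let *d* be the daily hazard of in-hospital death and *r* the daily hazard of discharge alive, both constant, with a 30-day horizon.
- True 30-day in-hospital mortality: CIF = d/(d+r) × [1 − exp(−30(d+r))]
- One minus Kaplan-Meier with discharge censored: 1 − exp(−30d)

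The second expression does not contain *r*, so the curve ignores how fast patients leave.

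**2. Two worked cases.**
- d = 0.02, r = 0.08: CIF = 0.2 × (1 − e^−3.0) = 19.0%; 1−KM = 1 − e^−0.60 = 45.1%.
- d = 0.015, r = 0.10: CIF = 0.1304 × (1 − e^−3.45) = 12.6%; 1−KM = 1 − e^−0.45 = 36.2%.

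**3. Range under constant hazards.** Fix the true in-hospital mortality and the fraction *s* still in hospital at day 30. Then d+r = −ln(s)/30 and d = CIF × (d+r)/(1−s). For CIF = 20% and s = 10%, 30d = 0.2 × 2.3026/0.9 = 0.5117, so 1−KM = 40.1%. With s from 20% down to 2%:

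| True in-hospital mortality | 1−KM, discharge censored |
|---|---|
| 10% | 18–33% |
| 15% | 26–45% |
| 20% | 33–55% |
| 30% | 45–70% |

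**4. Range when deaths come early.** Simulation of 200,000 subjects, 20% destined to die in hospital, exponential time to death, log-normal stay in survivors (log SD 0.6):

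| Mean days to death | Median stay of survivors (days) | True by day 30 | 1−KM, discharge censored | 1−KM, held event-free to day 30 |
|---|---|---|---|---|
| 3 | 14 | 19.9% | 21.0% | 19.9% |
| 3 | 9 | 20.0% | 24.1% | 20.0% |
| 5 | 9 | 19.9% | 34.3% | 19.9% |
| 8 | 9 | 19.7% | 47.7% | 19.7% |
| 8 | 6 | 19.5% | 75.8% | 19.5% |

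The excess runs from 21.0 − 19.9 = 1.1 points to 75.8 − 19.5 = 56.3 points. It is small when deaths precede most discharges and large when they overlap. The last column shows that holding discharged survivors event-free recovers the crude proportion.

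**5. Comparison between arms.**
- *False difference.* Give both arms 19.0% in-hospital mortality, with r = 0.08 in one and 0.05 in the other. The first needs d = 0.02 and the second d ≈ 0.0143. The curves read 45.1% and 34.9%, a spurious gap of 10.2 points against the arm that discharges faster.
- *Hidden difference.* Give both arms d = 0.02, with r = 0.08 and 0.12. Both curves read 45.1%, while in-hospital mortality is 19.0% and 0.1429 × (1 − e^−4.2) = 14.1%.

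**6. If the target were all-cause 30-day mortality.** With 20% in-hospital mortality and 10% still in hospital at day 30, the discharge-censored curve reads 40.1%. The true value is 20.0%, 25.8%, 31.0% or 40.1% when the post-discharge death hazard is 0, 0.25, 0.5 or 1.0 times the in-hospital hazard. At these multiples the curve is right only when discharge carries no information about risk. If vital status is actually observed to day 30, nobody is censored at discharge and the problem does not arise.

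**The case against.** The strongest reply is that SAP 9.2.2.3 contains no error as written. It does not say that discharge alive is censored. Holding discharged survivors event-free to day 30 is itself a Kaplan-Meier curve and fits the sentence. The SAP governs the analysis and presupposes 30 days of follow-up in several places (Section 2, 3.2, 9.2.2.1, 9.2.2.2, 9.2.2.5, 10.1). With vital status to day 30 there is no bias from discharge. The operative section also drops the in-hospital qualifier.

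Much of this stands. A reader might infer that the plan instructs censoring at discharge, or that the curves will certainly overstate mortality. The documents support neither: the rule is missing and the follow-up statements conflict. But the reply does not settle the matter. The protocol schedules no contact after discharge. It collects adverse events only for 72 hours plus 48 hours (Protocol 9.4 and 10.1), and SAP 10.1 says serious events are collected through 72 hours only. The SAP's 30-day language therefore has no clear data source, and with data ending at discharge, censoring there is what standard software and practice would do.

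A second objection is also fair. A reader might infer that the arm discharging earlier always shows a falsely higher curve. It does not: with equal death hazards the two curves coincide, and the error is then a concealed difference in in-hospital mortality (step 5 of the working).

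Finally, a reader might infer that the trial's mortality result is compromised. It is not. The tabulated percentages are crude, the intervals do not use Kaplan-Meier, and no test or decision rests on the curves.

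**Conclusion.** The concern holds as a gap in specification with a conditional bias. An in-hospital endpoint is paired with Kaplan-Meier, the protocol and SAP disagree on follow-up after discharge, and no rule covers subjects discharged alive. If they are censored at discharge, the curve overstates 30-day in-hospital mortality in every scenario examined. The size depends wholly on assumed timing and ranges from about 1 to more than 50 points. The direction is secure; no single figure within that range should be quoted as expected.

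The consequence is limited to descriptive displays. For MACE the same gap exists but is less certain. SAP 9.2.2.5 does not restrict MACE to the hospital stay, and with undefined components the extent to which other deaths compete cannot be judged.

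**What to change.** 1. Reconcile the protocol synopsis (Follow-up Schedule) and Table 1 with SAP Section 2, 3.2 and 10.1: state whether vital status and events are obtained after discharge up to day 30, and from what source.
2. In SAP 9.2.2.3, define the event, the time origin and the day-30 horizon, and use one endpoint name in SAP Section 2, 4.2.2.2 and 9.2.2.3.
3. For in-hospital mortality, plot the Aalen-Johansen cumulative incidence with discharge alive as a competing event, or hold subjects discharged alive event-free to day 30. With no other censoring, both end at the crude proportion in the table.
4. Keep Kaplan-Meier only for all-cause 30-day mortality, and only if vital status is known to day 30.
5. In SAP 9.2.2.5, define the MACE components, treat death outside the composite as a competing event, and treat discharge the same way if MACE is observed only in hospital.

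Items 2, 3 and 5 cost a paragraph of SAP text and a procedure option, with no new data and no change in sample size. Item 4 costs more only if vital status after discharge is not already being collected.
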